NCT02793817

Study ID: KPI-121-C-005

Study Title:

A Phase 3, Double-Masked, Randomized, Controlled Study to Evaluate the Safety and Efficacy of KPI-121 1.0% Ophthalmic Suspension in Subjects with Postsurgical Inflammation and Pain

Date: 24 Feb 2017

KALA PHARMACEUTICALS, INC. Clinical Protocol KPI-121-C-005

Project:

KPI-121

Compound Number/Name:

KPI-121

Protocol Number:

KPI-121-C-005

Protocol Title:

A Phase 3, Double-Masked, Randomized, Controlled Study to Evaluate the Safety and Efficacy of KPI-121

1.0% Ophthalmic Suspension in Subjects with

Postsurgical Inflammation and Pain

Sponsor:

Kala Pharmaceuticals, Inc. [name]

Medical Monitor:

Issue Date:

Original: 03 Feb 2016

Amendment 01: 03 May 2016 Amendment 02: 13 Jul 2016 Amendment 03: 23 Aug 2016 Amendment 04: 31 Jan 2017 Amendment 05: 24 Feb 2017

Approved:

24 February 2017

KALA PHARMACEUTICALS, INC. Clinical Protocol KPI-121-C-005 Investigator Signature Page

| Project: | KPI-121 |
|---------------------------------|---|
| Compound Number/Name: | KPI-121 |
| Protocol Number: | KPI-121-C-005 |
| Protocol Title: | A Phase 3, Double-Masked, Randomized, Controlled Study to Evaluate the Safety and Efficacy of KPI-121 1.0% Ophthalmic Suspension in Subjects with Postsurgical Inflammation and Pain |
| Sponsor: | Kala Pharmaceuticals, Inc. [name] |
| Issue Date: | Original: 03 Feb 2016 Amendment 01: 03 May 2016 Amendment 02: 13 Jul 2016 Amendment 03: 23 Aug 2016 Amendment 04: 31 Jan 2017 Amendment 05: 24 Feb 2017 |
| Contact for Serious Adverse Ev | ents: |
| Investigator Name (printed or t | yped): |
| Investigator's Signature: | |
| | Date |

SYNOPSIS

| Study Title: | KPI-121-C-005: A Phase 3, Double-Masked, Randomized, Controlled Study to Evaluate the Safety and Efficacy of KPI-121 1.0% Ophthalmic Suspension in Subjects with Postsurgical Inflammation and Pain | |
|---------------------------------------|---|--|
| Objectives: | The primary objective of the study is to investigate the efficacy and safety of KPI-121 1.0% ophthalmic suspension compared to placebo in subjects who have undergone cataract surgery. | |
| Study Population: | The study population will consist of subjects who have undergone routine uncomplicated cataract surgery and experience ocular inflammation postoperatively. | |
| Number of Subjects: | Approximately 720 subjects who are candidates for cataract surgery will be screened. One study eye from approximately 500 subjects will be randomized. | |
| Investigational Products: | KPI-121 1.0% ophthalmic suspension or placebo will be supplied as investigational product. | |
| Route and Duration of Administration: | 1 to 2 drops of investigational product will be instilled in the study eye two times per day (BID) for 14 ± 1 days. | |
| Study Design: | This is a Phase 3, multicenter, double-masked, randomized, placebo-controlled, parallel-group study designed to evaluate the efficacy and safety of KPI-121 1.0% ophthalmic suspension versus placebo in subjects who require treatment of postoperative anterior ocular inflammation. Approximately 720 subjects who are candidates for cataract surgery will be screened and approximately 500 subjects who, after undergoing routine, uncomplicated cataract surgery, present at Visit 3 (Day 1) with ≥ 2 anterior chamber cells in the study eye will be randomized in this study at approximately 35 centers located in the United States (US). Subjects who experience postoperative inflammation on the first day following routine, uncomplicated, cataract surgery and who meet all other eligibility criteria will be randomized to one of two study groups in an approximate 1:1 ratio to KPI-121 1.0% ophthalmic suspension dosed BID or placebo dosed BID. Investigational product or placebo will be initiated on the day following surgery and instilled as one to two drops in the study eye BID for 14 ± 1 days. | |

This study will include up to 7 clinic visits (including the surgery day) over 18 to 33 days total study duration. Visit 1 (Screening) will occur between 14 to 1 day(s) prior to surgery, and subjects who meet preoperative screening inclusion/exclusion criteria will be entered into the study. At Visit 2 (Surgery/Day 0) subjects will undergo routine cataract surgery according to the Investigator's normal procedures. Visit 3 (Randomization/Day 1) will occur on the day following surgery. Subjects who meet the qualifying postoperative randomization criteria will be eligible for randomization to one of the two study groups and will initiate investigational product on that day. Following randomization, subjects will be instructed to return to the clinic to be evaluated at Visit 4 (Day 4 ± 1 day), Visit 5 (Day 8 ± 1 day), and Visit 6 (Day 15 \pm 1 day). The last dose of investigational product will be administered upon completion of 14 days of evaluation. Following the End of Investigational Product Use Visit (Visit 6; Day 15 \pm 1 day), subjects will be asked to return to the clinic on Day 18 ± 1 day for Visit 7 (Follow-Up) and will be released from the study.

Assessments in this study will include:

- Subject-Rated Ocular Pain assessment
- Snellen Distance Visual Acuity (VA) by Pinhole Method
- Slit Lamp Biomicroscopy:
 - Signs of anterior ocular inflammation (cell and flare grading)
 - Palpebral conjunctival erythema, corneal edema, hyphema, ciliary flush, bulbar conjunctival injection
- Intraocular Pressure (IOP) Measurement
- Dilated Ophthalmoscopy
- Rescue Therapy Assessment
- Concomitant Medication Use Assessment
- Assessments of Adverse Events (AEs)

Efficacy Endpoint

Primary Efficacy Endpoints:

The primary endpoints of this study will be evaluated using hierarchical statistical testing in the following sequence:

1. Proportion of study eyes with complete resolution of anterior

chamber cells (grade = 0) at Visit 5 (Day 8 ± 1 day) maintained through Visit 6 (Day 15 ± 1 day) without receiving rescue medication prior to Visit 6 (Day 15 ± 1 day) as compared between KPI-121 1.0% ophthalmic suspension dosed BID and placebo dosed BID.

2. Proportion of study eyes with complete resolution of ocular pain (grade = 0) at Visit 5 (Day 8 ± 1 day) maintained through Visit 6 (Day 15 ± 1 day) without receiving rescue medication prior to Visit 6 (Day 15 ± 1 day) as compared between KPI-121 1.0% ophthalmic suspension dosed BID and placebo dosed BID.

Secondary Efficacy Endpoints:

- Proportion of study eyes with complete resolution of ocular pain (grade = 0) at Visit 4 (Day 4 ± 1 day) maintained through Visit 6 (Day 15 ± 1 day) without receiving rescue medication prior to Visit 6 (Day 15 ± 1 day) as compared between KPI-121 1.0% ophthalmic suspension dosed BID and placebo dosed BID. This endpoint will be tested at α = 0.0167.
- 2. Proportion of study eyes with complete resolution of anterior chamber flare (grade = 0) at Visit 4 (Day 4 ± 1 day) maintained through Visit 6 (Day 15 ± 1 day) without receiving rescue medication prior to Visit 6 (Day 15 ± 1 day) as compared between KPI-121 1.0% ophthalmic suspension dosed BID and placebo dosed BID. This endpoint will be tested at α = 0.0167.
- 3. Change from baseline in mean anterior chamber cell count at Visit 4 (Day 4 ± 1 day) as compared between KPI-121 1.0% ophthalmic suspension dosed BID and placebo dosed BID. This endpoint will be tested at $\alpha = 0.0167$.

Safety Endpoints

Assessment of AEs

Snellen Distance VA by Pinhole Method

Slit Lamp Biomicroscopy

IOP measurement

Dilated Ophthalmoscopy

Change from baseline to each post-surgery visit in ocular signs:

- Palpebral conjunctival erythema
- Corneal edema
- Hyphema
- Ciliary flush

| Bulbar conjunctival injection | | | |
|-------------------------------|--|--|--|
| Eligibility Criteria: | Inclusion Criteria: | | |
| Eligibility Criteria: | Inclusion Criteria: At Visit 1, individuals of either gender or any race will be eligible for study participation if they: Provide written informed consent and Health Insurance Portability and Accountability Act (HIPAA) authorization prior to any study-related procedures. Are 18 years of age or older. Are willing and able to follow instructions and can be present for the required study visits for the duration of the study. Are candidates for routine, uncomplicated cataract surgery [e.g., phacoemulsification with posterior chamber intraocular lens (IOL) implantation, not combined with any other surgery]. In the Investigator's opinion, have potential postoperative Snellen Distance VA by pinhole method of at least 20/200 in the study eye. Are women of child bearing potential (WOCBP) who are not pregnant or lactating and not sexually active (i.e., abstinent) for 14 days prior to Visit 1 and are willing to remain so through 30 | | |
| | | | |
| | completion of the subject's first menstrual cycle following last administration of the investigational product, whichever period of time is longer. b. Barrier method (condom or diaphragm) with spermicide for at least three months prior to Visit 1 through Visit 6 or last administration of the investigational product or until completion of the subject's first menstrual cycle | | |

- following last administration of the investigational product, whichever period of time is longer.
- c. Stable hormonal contraceptive for at least three months prior to Visit 1 through Visit 6 or last administration of the investigational product or until completion of the subject's first menstrual cycle following administration of the investigational product, whichever period of time is longer.

NOTE: For Depo-Provera injection contraceptives, the statement regarding first menstrual cycle following administration of the investigational product is not applicable as females receiving this form of contraception will not have menses.

- d. In a monogamous relationship with a surgically sterilized (i.e., vasectomized) partner for at least six months prior to Visit 1 through Visit 6 or last administration of the investigational product or until completion of the subject's first menstrual cycle following administration of the investigational product, whichever period of time is longer.
- 7. Are postmenopausal women who have had no menstrual cycle for at least one year prior to Visit 1 or are women who have undergone one of the following sterilization procedures at least 6 months prior to Visit 1:
 - a. Bilateral tubal ligation
 - b. Hysterectomy
 - c. Hysterectomy with unilateral or bilateral oophorectomy.
 - d. Bilateral oophorectomy

Exclusion Criteria:

In order for subjects to be eligible at Visit 1 they may not:

- 1. Require concurrent ocular therapy (either eye) with nonsteroidal anti-inflammatory drugs (NSAIDs), mast cell stabilizers, antihistamines, or decongestants within 2 days prior to surgery and for the duration of the study.
- 2. Require treatment with systemic NSAIDs, with the exception of ≤ 81 mg/day of acetylsalicylic acid (ASA or aspirin), within 2 days prior to surgery and for the duration of the study.

- 3. Require treatment with systemic (except stable maintenance dose of inhaled or intranasal corticosteroids) or ocular (either eye) corticosteroids (other than investigational product) within 14 days prior to cataract surgery and for the duration of the study.
- 4. Require concurrent systemic or ocular therapy with immunosuppressants (with the exception of oral corticosteroids less than prednisone 11 mg/day or equivalent) within 30 days prior to surgery and for the duration of the study.
- 5. Require change in treatment with anticholinergics or oral corticosteroids (dose must be less than prednisone 11 mg/day or equivalent) within six months prior to Visit 1.
- 6. Require change in stable treatment with antidepressants within 6 months prior to Visit 1.
- 7. Require change in use of nutraceuticals or multivitamins during trial participation.
- 8. Have known hypersensitivity or contraindication to the investigational product(s) or their components.
- 9. Use any topical ophthalmic medications including glaucoma medications, all eye drops (except antibiotic eye drops considered to be included in post cataract surgery standard of care treatment), all gels or artificial tears within 2 days prior to surgery and for the duration of the study. Note: Besifloxacin Ophthalmic Suspension is not permitted within 2 days prior to surgery or for the duration of the study.
- 10. Use any topical eyelash growth medications within 7 days prior to surgery and for the duration of the study.
- 11. Have history of glaucoma, IOP >21 mmHg at the screening or randomization visit(s), or are being treated for glaucoma in either eye.
- 12. Wear contact lenses for 4 weeks prior to Visit 1 and throughout the study.
- 13. Be monocular or have Snellen Distance VA by pinhole method of 20/200 or worse in the non-study eye.
- 14. Have had penetrating intraocular surgery in the study eye within 3 months or within two weeks in the fellow eye.
- 15. Have had corneal refractive surgery or corneal transplantation (full thickness, anterior, or posterior) within the past year or are unstable and/or require medication.
- 16. Have a diagnosis of:

- a. Ongoing ocular infection.
- b. Severe/serious ocular condition that in the judgment of the Investigator could confound study assessments or limit compliance.
- c. Severe/serious systemic disease or uncontrolled medical condition that in the judgment of the Investigator could confound study assessments or limit compliance.
- 17. Have been exposed to an investigational drug within 30 days prior to screening or up to 18 days following surgery.
- 18. Be an employee of the site that is directly involved in the management, administration, or support of this study or be an immediate family member of the same.
- 19. Have a known history of alcohol and/or drug abuse.
- 20. In the opinion of the Investigator or study coordinator, be unwilling or unable to comply with the study protocol or unable to successfully instill eye drops.

Randomization Criteria:

To qualify for randomization at Visit 3 (Postoperative Day 1), a subject must:

- 1. Have undergone routine, uncomplicated cataract surgery (e.g., phacoemulsification with posterior chamber IOL implantation, not combined with any other surgery).
- 2. Have \geq Grade 2 anterior chamber cells.
- Continue to meet inclusion/exclusion criteria with respect to current ocular and medical conditions (Sections 4.1 and 4.2), and must not have taken prohibited medications (Section 6.2.2).

TABLE OF CONTENTS

| LIST OF A | ABBREVIATIONS AND DEFINITIONS OF TERMS | . 15 |
|-----------|---|------|
| 1. | INTRODUCTION | . 17 |
| 1.1. | DESCRIPTION OF INVESTIGATIONAL PRODUCT | . 18 |
| 1.2. | JUSTIFICATION FOR ROUTE OF ADMINISTRATION AND DOSE SELECTION | . 19 |
| 1.3. | GCP COMPLIANCE | . 19 |
| 1.4. | POPULATION TO BE STUDIED. | . 19 |
| 2. | TRIAL OBJECTIVES AND PURPOSE | . 20 |
| 2.1. | OBJECTIVE | . 20 |
| 3. | TRIAL DESIGN | . 21 |
| 3.1. | PRIMARY EFFICACY ENDPOINTS | . 21 |
| 3.2. | SECONDARY EFFICACY ENDPOINTS | . 21 |
| 3.3. | SAFETY ENDPOINTS | . 21 |
| 3.4. | DESCRIPTION OF TRIAL DESIGN | . 22 |
| 3.4.1. | Investigational Product | . 24 |
| 3.4.2. | Methods to Minimize Bias | . 26 |
| 4. | SELECTION OF SUBJECTS | . 27 |
| 4.1. | SUBJECT INCLUSION CRITERIA. | . 27 |
| 4.2. | SUBJECT EXCLUSION CRITERIA | . 28 |
| 4.3. | RANDOMIZATION CRITERIA | . 30 |
| 5. | PROCEDURES | . 31 |
| 5.1. | VISIT DESCRIPTIONS | . 31 |
| 5.1.1. | Visit 1: Screening Visit (Day -14 to Day -1) | . 31 |
| 5.1.2. | Visit 2: Surgery Visit (Day 0) | . 31 |
| 5.1.3. | Visit 3: Randomization Visit (Day 1) | . 32 |
| 5.1.4. | Visit 4: Study Visit (Day 4 ± 1 day) | . 33 |
| 5.1.5. | Visit 5: Study Visit (Day 8 ± 1 day) | . 34 |
| 5.1.6. | Visit 6: End of Investigational Product Use (Day $15 \pm 1 \text{ day}$) | . 34 |
| 5.1.7. | Visit 7: Follow-Up Visit (Days 18 ± 1 day) | . 35 |
| 5.1.8. | Early Termination Visit | . 35 |

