3.2. SECONDARY EFFICACY ENDPOINTS

- Proportion of study eyes with complete resolution of ocular pain (grade = 0) at Visit 4
 (Day 4 ± 1 day) maintained through Visit 6 (Day 15 ± 1 day) without receiving rescue
 medication prior to Visit 6 (Day 15 ± 1 day) as compared between KPI-121 1.0%
 ophthalmic suspension dosed BID and placebo dosed BID. This endpoint will be tested at
 α = 0.0167.
- 2. Proportion of study eyes with complete resolution of anterior chamber flare (grade = 0) at Visit 4 (Day 4 ± 1 day) maintained through Visit 6 (Day 15 ± 1 day) without receiving rescue medication prior to Visit 6 (Day 15 ± 1 day) as compared between KPI-121 1.0% ophthalmic suspension dosed BID and placebo dosed BID. This endpoint will be tested at $\alpha = 0.0167$.
- 3. Change from baseline in mean anterior chamber cell count at Visit 4 (Day 4 ± 1 day) as compared between KPI-121 1.0% ophthalmic suspension dosed BID and placebo dosed BID. This endpoint will be tested at $\alpha = 0.0167$.

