9.2. SAMPLE SIZE ESTIMATION

A two group χ^2 test with a 0.05 two-sided significance level will have 99% power to detect the difference between a proportion with complete resolution of anterior chamber cells in the active group of 0.31 and the placebo group proportion of 0.15 when the sample size in each group is 250. The power is the same for the complete resolution of pain endpoint.

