9.3. LEVEL OF SIGNIFICANCE

The primary assessment will be evaluated using a 5% level of significance using the hierarchical testing described in Section 9.1.2 Analysis of Efficacy.

All other reported p-values will be considered descriptive and hypothesis generating.

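### If the three secondary tests are meant to carry inferential weight, Holm's step-down procedure would spend their alpha better than a fixed 0.0167 each, provided a gate and a matching edit to Section 9.3 come with it

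*Combined protocol and SAP*

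**What the plan says.** The synopsis and Section 3.2 list three secondary endpoints: sustained pain resolution from Visit 4, sustained flare resolution from Visit 4, and a third, "Change from baseline in mean anterior chamber cell count at Visit 4". Each carries the same sentence: "This endpoint will be tested at α = 0.0167". Neither place states whether these tests are one- or two-sided.

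The only multiplicity procedure in the statistics section is the fixed sequence for the two primaries (cells, then pain) in Section 9.1.2. Section 9.3 confirms it: "The primary assessment will be evaluated using a 5% level of significance using the hierarchical testing described in" Section 9.1.2. Section 9.3 then adds: "All other reported p-values will be considered descriptive and hypothesis generating".

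No step-down rule, no passing on of alpha between endpoints, and no gate from the primaries to the secondaries is described. Section 9.2 gives power for the primaries only.

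**The concern.** Since 0.05/3 = 0.0167 to four decimals, the plan applies plain Bonferroni to a family of three. Each endpoint keeps the same threshold whatever the other two show. An endpoint with a p-value between 0.0167 and 0.05 therefore fails even when the other two are clearly positive, although a standard procedure with the same 0.05 bound could declare it significant.

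This matters only if the secondaries are meant to support claims. Giving each a test level implies that they are; Section 9.3 implies that they are not. No primary result depends on the answer.

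**Working it through.** **Inputs from the documents.** Three secondary endpoints at 0.0167 each (synopsis, Section 3.2). Section 9.2: "test with a 0.05 two-sided significance level will have 99% power", for proportions "in the active group of 0.31 and the placebo group proportion of 0.15", "when the sample size in each group is 250". Two-sided tests are assumed for the secondaries, as for the primaries.

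**Step 1. Reproduce the plan's own figure.** Power = Φ[(Δ − z·SE0)/SE1], with Δ = 0.31 − 0.15 = 0.16 and pooled proportion 0.23.
- SE0 = √(2 × 0.23 × 0.77/250) = 0.0376
- SE1 = √((0.31 × 0.69 + 0.15 × 0.85)/250) = 0.0370
- At α = 0.05, z = 1.960: (0.16 − 1.960 × 0.03764)/0.03695 = 2.33, power 0.990.

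The stated 99% reproduces.

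**Step 2. Identify the split.** 0.05/3 = 0.016667, rounded to 0.0167. The sum 3 × 0.0167 = 0.0501 is a rounding excess only.

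**Step 3. Compare the rules.** Order the p-values from smallest to largest.

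| Rank of p-value | Plan | Holm |
|---|---|---|
| Smallest | 0.0167 | 0.05/3 |
| Middle | 0.0167 | 0.05/2 = 0.025 |
| Largest | 0.0167 | 0.05 |

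Holm stops at the first failure. Its bound holds under any dependence: with m true nulls, the first true null reached faces a threshold of at most 0.05/m, so a false rejection needs some true-null p-value at or below 0.05/m. That has probability at most m × 0.05/m = 0.05.

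- p = 0.001, 0.010, 0.030: two wins under the plan, three under Holm.
- p = 0.020, 0.030, 0.040: none under either, because the smallest must still pass 0.05/3.

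**Step 4. Single-test power at the three levels, 250 per group.**

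| Proportions | 0.0167 | 0.025 | 0.05 |
|---|---|---|---|
| 0.31 vs 0.15 (Section 9.2) | 0.971 | 0.980 | 0.990 |
| 0.25 vs 0.15 (assumed) | 0.657 | 0.712 | 0.800 |

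**Step 5. Joint behaviour.** Simulation of three correlated normal test statistics, 400,000 runs per scenario. The documents give no effect sizes, standard deviations or correlations for the secondaries, so power and correlation are assumptions. The third endpoint is a mean change, so using the Section 9.2 effect for it is only a stand-in.

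| Power of each at 0.0167 | Correlation | Each endpoint, plan → Holm | All three, plan → Holm |
|---|---|---|---|
| 80% | 0 | 80% → 88% | 51% → 72% |
| 80% | 0.6 | 80% → 86% | 63% → 78% |
| 97% (0.31 vs 0.15) | 0 | 97% → 99% | 92% → 97% |
| 97% (0.31 vs 0.15) | 0.6 | 97% → 99% | 93% → 97% |

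The chance of at least one win is the same under both rules in every row, apart from rounding.

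**Step 6. Attained error.** With all three nulls true and correlation 0, the family-wise error is 0.0495 under the plan and 0.0494 under Holm. With one true null beside two real effects (90% power each at 0.0167), the null endpoint is rejected with probability 0.017 under the plan, against 0.046 (correlation 0) or 0.041 (correlation 0.6) under Holm. All stay within 0.05.

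**Step 7. Whole-trial error.** The primaries already use the full 0.05. A second family at 0.05 with no gate gives a trial-wide bound of 0.05 + 0.05 = 0.10, under Bonferroni and Holm alike.

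**The case against.** The strongest reply is that Section 9.3 makes the secondaries descriptive. If it governs, the fixed level costs no claim and Holm wins none. That stands: the point is conditional, and Section 9.3 has to be reconciled with the synopsis and Section 3.2 first. It does not justify the fixed split itself, because dividing alpha serves a purpose only when the tests carry weight.

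Second, Bonferroni is valid and pre-specified, gives simple simultaneous intervals, and lets each endpoint stand without reference to the others. That also stands. A reader might infer that the plan is in error or its secondary results uninterpretable; nothing in the documents supports this.

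Third, a reader might take Holm to be free of any cost in error. Only the bound is unchanged; Step 6 shows that the attained error rises when some effects are real.

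Fourth, a reader might take the 80% scenario as the expected gain. The documents do not support that either: the only effect size they give yields about two points per endpoint. Nor is that figure a forecast. The pain secondary requires resolution from Visit 4 rather than Visit 5, so its responders are a subset of the primary pain responders, and a smaller difference is plausible.

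**Conclusion.** The point holds in conditional form. If the three secondary tests are inferential, the fixed 0.0167 is dominated by Holm at the same 0.05 bound, apart from p-values between 0.016667 and 0.0167. The gain falls on the second and third endpoints only. It runs from about 97% to 99% per endpoint at the Section 9.2 effect, to 80% rising to 86-88% each and 51-63% rising to 72-78% for all three at an assumed 80% power (correlations 0 to 0.6).

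A reader might infer that replacing the 0.0167 sentences is enough to support secondary claims. It is not: Section 9.3 would still call those p-values descriptive, and without a gate the trial-wide bound would be about 0.10. This is an optional efficiency improvement on secondary endpoints and leaves the primary analysis as it is.

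**What to change.** Make three linked edits before unmasking.

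1. In the synopsis and Section 3.2, replace the three sentences that fix 0.0167 with: *If both primary endpoints are significant, the three secondary endpoints will be tested with Holm's step-down procedure at a family-wise two-sided alpha of 0.05 (ordered p-values compared with 0.05/3, 0.05/2, 0.05).* This also states the sidedness and removes the rounding excess.
2. Amend Section 9.3 so that only p-values outside the primary hierarchy and this secondary family are descriptive.
3. Carry the same rule into Section 9.1.2, which now covers the primaries only.

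If the sponsor instead intends the secondaries to be descriptive, the alternative is to keep Section 9.3 and delete the 0.0167 levels; Holm is then unnecessary.

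No extra subjects, visits or data are needed. The costs are less simple multiplicity-adjusted confidence intervals, a higher attained error within the 0.05 bound, and no secondary claims if either primary fails. If the 99% power in Section 9.2 is right for both primaries, the chance that the gate stays closed is at most 1% + 1% = 2%.
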